4.4 Conventions

All data listings, summaries, and figures will be generated using SAS version 9.4 or higher¹.

Summaries will be presented by Part (A/B), Cohort (and by dose within Cohort for adverse events [AEs]), and overall. Treatment group labels will be displayed as follows:

Part A					
	Cohort 1	Cohort 2	Cohort 3	Cohort 4	Overall

Template: WCT-TP-ST-005-005 Page 11 of 24 Effective Date: 15-Apr-2016 Confidential

Listings will be sorted in the following order: Part, Cohort, participant ID, parameter, and cycle unless otherwise stated.

Continuous variables will be summarized by the number of non-missing observations, mean, median, standard deviation, minimum and maximum.

Categorical variables will be summarized by presenting the frequency and percent. Percentages will be based on the number of non-missing observations or the participant population unless otherwise specified. For each variable, all categories will be shown. Zero frequencies (but not the percent) within a category will be presented.

4.5 **Decimal Places**

Decimal places for derived data described in section 4.2 will be determined by the scale of measurement unless otherwise stated. No decimal places will be displayed if the smallest calculated value is \geq 100; 1 decimal place will be displayed when the smallest value is within the interval (10, 100), with 10 being inclusive; 2 decimal places will be displayed when the smallest value is within (1, 10), with 1 being inclusive; and so on for even smaller scales of measurement.

Derived data where it is known in advance the result will be an integer for example day, month, year, number of days and total scores (for rating scales) will be presented with zero decimal places.

Means, medians and percentiles will be displayed to one more decimal place than the data, dispersion statistics (e.g. standard deviation) will have two more decimal places, and the minimum and maximum will be displayed to the same number of decimal places as reported in the raw data. Percentages will be displayed with one decimal place.

4.6 **Disposition**

Participant disposition will be summarized as follows:

• The number of participants included in the Screened Population and the Safety Population will be summarized by Part, Cohort and overall for the Screened Population.

Template: WCT-TP-ST-005-005 Page 12 of 24 Effective Date: 15-Apr-2016 Confidential

- The number of participants who failed screening and the reasons for failure will be tabulated by Part, Cohort and overall for the Screened Population.
- The number of participants who completed the treatment period, completed the study, and who prematurely withdrew along with the reasons for withdrawal will be tabulated by Part, Cohort and overall for the Safety Population. Early withdrawals will also be summarized by the dose the participant was on at the time of withdrawal.
- The number of participants who completed each treatment cycle of the study will be summarized by Part, Cohort and overall for the Safety Population.
- A listing of participant disposition will be produced for the Enrolled Population.
- A listing of participants by Investigator name and treatment group will be produced for the Screened Population.

4.7 Protocol Deviations

Important protocol deviations and protocol deviations related to COVID-19 will be listed using the Safety Population.

4.8 Baseline Comparability

Demographics and baseline variables will be summarized by Part, Cohort and overall using the Safety Population.

The comparability of treatment Part and Cohorts with respect to participant demographics and baseline characteristics will be assessed in a descriptive manner, but no formal statistical testing will be performed.

4.9 **Demographics**

The following baseline demographic variables will be summarized using standard continuous or categorical variable summaries: age at Informed Consent (years) both continuous and categorized as <18 years, ≥18 years), sex, race, ethnicity, height, weight, and body surface area (BSA). Additionally, a summary of participant characteristics for disclosure to public databases

Template: WCT-TP-ST-005-005 Page 13 of 24 Effective Date: 15-Apr-2016 Confidential

(gender, race, ethnicity, age) will be produced for the Safety Population. The following age categories will be summarized:

- Newborns (0-27 days)
- Infants and toddlers (28 days 23 months)
- Children (2-11 years)
- Adolescents (12-17 years)
- Adults (between 18 and 64 years)
- From 65 to 84 years
- 85 years and older

A listing of baseline demographic variables will be produced for the Safety Population.

4.10 Medical History

Previous and ongoing medical history conditions and previous surgical and medical procedures reported at screening will be presented together in a single table by Medical Dictionary of Regulated Activities (MedDRA) v24.0 primary System Organ Class (SOC) and Preferred Term (PT) and summarized by Part, Cohort and overall for the Safety Population. A listing of these data will also be produced.

Baseline disease characteristics related to PROS and PS (life stage overgrowth reported, any significant family history, disease diagnosis, and time since diagnosis [years]) will be summarized in a separate table and listing using the Safety Population.

The pathological diagnosis (genetic testing results) will be summarized in listing format only using the Safety Population.

A listing of all non-drug procedures related to PROS or PS will be produced using the Safety Population.

4.11 Prior and Concomitant Medications

Separate tabulations will be produced for prior and concomitant medications presented by Part, Cohort and overall for the Safety Population. Prior medications are defined as all medications

Template: WCT-TP-ST-005-005 Page 14 of 24 Effective Date: 15-Apr-2016 Confidential

taken within 45 days of the first dose of miransertib. Concomitant medications are defined as medications taken on or after the date of first dose of study drug. Concomitant medications will be coded using the World Health Organization (WHO) Drug Dictionary, version B3 WHO Drug Global – March 2021, and will be summarized using ATC Level 2 and PT. A listing of these data will also be produced.

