#### 5 STUDY PROCEDURES

# 5.1 Medical History

Medical history will include but not be limited to the following:

- Demography: date of birth, sex, race and ethnicity
- Clinically significant prior diagnoses and surgical operations (not related to PROS or PS)
- Medications used within 45 days before the first dose of miransertib and throughout the treatment period should be reported
- Natural history of the disease (up to the study enrollment):
  - Perinatal history; prenatal and postnatal evaluations; family history; intellectual
    and psychomotor developmental milestones; disease-related manifestations
    (anatomical location, severity, frequency); management of the disease,
    including prophylactic and symptomatic therapies, hospitalizations, surgical
    operations; results of the clinical function assessments
- Genetic testing results: AKT1 or PIK3CA mutation status in the affected tissue must be confirmed before dosing. The AKT1 or PIK3CA mutation (dependent on clinical diagnosis) results will be captured in the EDC database and copies of the genetic report will be forwarded to the Sponsor or designee. If mutational status is unknown, archival or fresh tissue biopsy must be collected and tested for mutation status to confirm eligibility for the study.
  - An archival tissue sample is to be sent to the Sponsor or designee for central confirmation of mutation analysis, if required.
- When possible, imaging scans (eg, MRI, CT, US), photography, video recordings, and/or other assessments of size such as linear and/or circumference measurements performed before study enrollment will be collected and forwarded to the Sponsor or designee.

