4.3.1 Missing/Partial Start/Stop Date of Adverse Events and Concomitant Medications

Missing and partial start and stop date will be imputed for analysis purposes as follows.

Partial or missing stop date will be imputed as follows:

If the stop date is completely missing and the event has resolved or the participant has stopped taking the concomitant medication, the stop date will be imputed as the date of the participant's last clinic visit in the study.

- If only the year is known, the stop date will be imputed as "31-Dec" of that year or as the date of the participant's last clinic visit in the study if in the same year.
- If the month and year are known, the stop date will be imputed as the last day of that month unless the stop date corresponds to the same month as the participant's last clinic visit in which case the date of participant's last clinic visit in the study will be used instead.

Missing start date will be imputed as follows:

• If the stop date occurs on or after the start of study drug or the event/concomitant medication is ongoing, the start date will be imputed as the date of the first dose of study drug.

Template: WCT-TP-ST-005-005 Page 9 of 24 Effective Date: 15-Apr-2016 Confidential

• If the stop date occurs before the start of study drug, the start date of the event/concomitant medication will be imputed as the participant's screening date or the stop date of the event/concomitant medication whichever the earlier.

Partial start date (year present, but month and day missing)

- If the stop date occurs on or after the start of study drug or the event/concomitant medication is ongoing, and the year is the same as the year of first dosing the start date will be imputed as "01-Jan" of the same year or the date of the first dose of study drug whichever is latest. If the year is different from the year of first dosing "01-Jan" will be used.
- If the stop date occurs before the start of study drug, the start date of the event/concomitant medication will be imputed as the "01-Jan" of the same year.

Partial start date (month and year present, but day missing)

- If the stop date occurs on or after the start of study drug or the event/concomitant medication is ongoing, the start date will be imputed as the first day of the same month and year unless this partial start date is in same month as the first dose of study drug in which case the date of first dose of study drug will be used.

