- If the stop date occurs before the start of study drug, the start date will be imputed as the first day of the month and year of the partial stop date.

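### SAP 4.11 omits 'before' from the 45-day prior-medication window, and under the 'before' reading the Day 1 imputation in SAP 4.3.1 removes some background drugs from the prior-medication table

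*SAP*

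**What the plan says.** SAP 4.11 plans two tables: "Separate tabulations will be produced for prior and concomitant medications presented by Part, Cohort and overall for the Safety Population". Prior medications are those "taken within 45 days of the first dose of miransertib". The next definition reads: "Concomitant medications are defined as medications taken on or after the date of first dose of study drug". Protocol 5.1 sets the collection window with an explicit direction: "Medications used within 45 days before the first dose of miransertib and throughout the treatment period should be reported". SAP section 7, which lists departures from the protocol's planned analysis, does not mention this difference.

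SAP 4.3.1 gives one set of start-date rules for adverse events and medications together. Where the item is ongoing or stopped on or after first dose:

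- Start wholly missing: "the start date will be imputed as the date of the first dose of study drug".
- Year only, same year as first dose: 1 January "or the date of the first dose of study drug whichever is latest".
- Month and year only, same month as first dose: "in which case the date of first dose of study drug will be used".

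Items that stopped before first dose, and partial dates from an earlier year or month, keep a start before dosing. Under SAP 4.3, all these rules give way where other eCRF data disagree, and participant listings show dates as recorded.

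**The concern.** Programmers work from the SAP text, and 4.11 can be read in two ways. A window on both sides of first dose puts drugs begun on treatment into a table meant to show background therapy. A window before first dose gives the right table only if the start dates fed into it are suitable for that purpose.

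The Day 1 rule is cautious for adverse events, because an event of unknown onset becomes treatment-emergent. For medications it works differently: an ongoing drug of unknown start is treated as begun on Day 1 and so as not taken beforehand. At stake is the only table the SAP plans of drug therapy before miransertib. SAP 4.10 tabulates medical history conditions and procedures, not drugs.

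**Working it through.** The plan gives no figure to reproduce. The check applies the SAP 4.3.1 rules to test records and classifies each record under both readings of 4.11.

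**Inputs.** The window (45 days) is from SAP 4.11 and Protocol 5.1, and the imputation rules are from SAP 4.3.1. Assumed for illustration: first dose F = 15 June 2020, screening 14 days earlier, and no other eCRF data that contradict the imputed date.

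**Classification.**

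- Prior, 'before' reading: start < F and stop ≥ F − 45 days.
- Prior, literal reading: start ≤ F + 45 days and stop ≥ F − 45 days.
- Concomitant, either reading: stop ≥ F. An ongoing drug always satisfies the stop condition.

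**The year-only rule.** Any F in a given year is on or after 1 January of that year. The later of the two dates is therefore always F, so every year-only start in the first-dose year becomes Day 1 for a drug not stopped before dosing.

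**Results.** Days are relative to F. Arrows run from the status with the true start to the status with the imputed start.

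| True start | Start as recorded | Stop | Start used | Prior, 'before' | Prior, literal | Concomitant |
|---|---|---|---|---|---|---|
| −1100 | missing | ongoing | 0 | yes → **no** | yes → yes | yes |
| −1100 | complete | ongoing | −1100 | yes | yes | yes |
| −150 | year only, 2020 | ongoing | 0 | yes → **no** | yes → yes | yes |
| −12 | June 2020 | ongoing | 0 | yes → **no** | yes → yes | yes |
| −400 | year only, 2019 | ongoing | −531 | yes → yes | yes → yes | yes |
| −30 | May 2020 | ongoing | −45 | yes → yes | yes → yes | yes |
| −500 | missing | −10 | −14 | yes → yes | yes → yes | no |
| +20 | complete | ongoing | +20 | no | **yes** | yes |
| +60 | complete | ongoing | +60 | no | no | yes |
| +200 | missing | ongoing | 0 | no → no | no → **yes** | yes |

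Under the 'before' reading, the three date patterns that map to Day 1 each lose a true background drug. Under the literal reading no background drug is lost, but a drug begun on day +20 counts as prior, and so does one begun on day +200 with a missing start. The two kinds of error belong to different readings and do not occur together. Concomitant status depends only on the stop date, so it is correct in every row.

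**The last bullet of 4.3.1.** For a drug that stopped before dosing and whose start lacks only the day, "the start date will be imputed as the first day of the month and year of the partial stop date". This discards a recorded start month. It cannot change prior status, because a drug that stopped before F is prior exactly when its stop date is within 45 days before F.

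**The case against.** The strongest case against is that this is little more than an omitted word. The category is called prior, the next definition begins at first dose, and Protocol 5.1 says before, so few would program a two-sided window. That stands as to intent, and the literal reading is the less likely one. It does not dispose of the point, because the intended reading is the one under which the Day 1 rule removes background drugs.

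The second argument is the eCRF override in SAP 4.3. Concomitant medications are recorded at Screening in Protocol Tables 3 and 4 and in the Part A schedule in Annex 1. A drug recorded there could contradict a Day 1 start. This stands in part: it is too absolute to say that an ongoing drug with a missing start can never be prior. But the SAP does not say that a Screening record counts as a contradiction, nor do the documents say whether the eCRF keeps the visit link.

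A reader might infer more than the documents support:

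- *All unknown starts move to Day 1.* They do not. The drug must be ongoing or stopped on or after first dose, and a partial date from an earlier year or month stays before dosing.
- *The prior table is wrong under either reading.* Under the 'before' reading, errors need incomplete dates that other eCRF data do not contradict. The number of such records could be zero.
- *Background drugs will look like treatment for drug effects.* No planned output shows this. The medication summaries are by drug class and preferred term, listings carry recorded dates, and these drugs belong in the concomitant table whatever their start.
- *About half of year-only records are misclassified.* That needs start and first-dose dates spread evenly and independently over the year. Nothing in the documents supports it.

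Finally, the fix introduces an opposite error. A drug of wholly unknown start could have been first taken late in a treatment period of up to 48 × 28 = 1,344 days and would still count as prior. This stands, and it is the price of the change.

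**Conclusion.** The point holds as a minor one. The SAP window lacks the protocol's direction. Under the intended direction, a stated imputation rule works against the table it feeds: for three date patterns, a drug not stopped before first dose is removed from the prior-medication table, subject to the eCRF override.

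The effect is limited to that descriptive table. The concomitant table, the listings and the adverse event analyses do not change. Its size cannot be estimated, because neither document gives the share of medication records with incomplete starts. The conclusion assumes that imputed dates are used to assign prior status, which follows from 4.3.1 imputing for analysis purposes, and that the eCRF does not otherwise show earlier use.

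**What to change.** 1. In SAP 4.11, define prior medications as those *taken at any time in the 45 days before the first dose in this study*. This restores the protocol's direction. It also fixes the reference dose for Cohort 4, whose participants may have taken miransertib before enrolling.
2. In SAP 4.3.1, state that the Day 1 imputation is not used to decide prior status. Count a medication that is ongoing or stopped on or after first dose as both prior and concomitant, unless its recorded date parts or other eCRF data show a start on or after first dose. Say that a Screening record counts as evidence of earlier use.
3. Optional, with no effect on prior status: in the last bullet of 4.3.1, use the recorded start month in place of the stop month.

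The cost is two or three sentences and no new data. The downside is that some drugs of unknown start that truly began on treatment will also appear in the prior table. A footnote giving the number of records classified this way would let a reader judge the effect.

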4.12 Exposure to Study Drug

Duration of exposure is defined as the total number of days of study drug administration, ignoring any temporary drug interruption. Duration of exposure will be presented by Part, Cohort, and overall for the Safety Population.

Additionally, the total (cumulative) amount of administered treatment, dose intensity, and relative dose intensity will be summarized for the Safety Population. The amount of administered treatment will be calculated for each capsule strength as follows:

- Total amount of 5 mg dose received per cycle = 5 * [(total # of 5 mg capsules dispensed)
 (total # of 5 mg capsules lost + total # of 5 mg capsules returned)
- Total amount of 10 mg dose received per cycle = 10 * [(total # of 10 mg capsules dispensed) (total # of 10 mg capsules lost + total # of 10 mg capsules returned)

The total (cumulative) amount of administered treatment will be calculated as the sum of the total amount of 5 mg and 10 mg doses received across all cycles and for the entire study duration.

Relative dose intensity (expressed in mg/m²) will be summarized using descriptive statistics and will present the number and percentage of participants receiving at least one dose at each level (i.e., 5 mg/m² daily, 10 mg/m² daily, etc.). Dose intensity (expressed in mg) is defined as the total dose received, calculated using relative dose intensity and BSA. Total dose received will be summarized using descriptive statistics.

Exposure data will also be listed using the Safety Population.

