Miransertib will be supplied as 5 and 10-mg capsules, which should be taken either 1 hour before or 2 hours after a meal. Capsules should be swallowed whole. The preferred beverage for administration is water. However, in cases where there is a medical problem affecting the participant's ability to swallow (eg, the participant has an enlarged tongue), the capsules can be opened, and the powder contents sprinkled onto a small amount of sweetened semiliquid food (eg, apple sauce, chocolate syrup, or ice cream) and administered in its entirety to the participant. The same type of semiliquid food should be used, if possible, for the duration of the study. Refer to the Pharmacy Manual for specific instructions on opening the capsules. To maximize safety and avoid unnecessary exposure to the drug by caregivers, it is recommended that gloves and a facemask be worn by the caregiver when handling opened capsules and that the gloves and facemask are discarded along with the empty capsule shells after use. Pregnant women should not open the capsules.

Miransertib will be administered once daily. Dose will be calculated based on BSA, and actual dose level will be rounded to the nearest 5 mg using a dosing nomogram (Appendix 2). Miransertib will be capped at a BSA >1.77 m^2. During site visits, miransertib dosing will be adjusted for changes in BSA according to the dosing nomogram.

Participants and/or their guardians must use the diary card provided to keep a record of daily intake of each dose of miransertib and the method of administration (capsules swallowed whole or opened and swallowed with semiliquid).

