#### 9.4 Safety Analysis

All participants who receive at least one dose of study treatment will be evaluated for safety. The incidence rates of TEAEs, treatment-related adverse events, and serious adverse events (SAEs will be described, as identified with preferred terms and MedDRA system organ class.

The frequency of occurrence of overall toxicity, categorized by the maximum toxicity grades (severity), will also be described. Listings of laboratory test results and CTCAE grades will be generated, and descriptive statistics summarizing the changes in laboratory tests over time will be presented.

The safety analyses will be presented by dose and overall using the Safety Population. Safety assessments include AEs, 12-lead ECGs, physical examination, clinical laboratory, and home fasting glucose measurements.

Adverse events will be graded according to the current version of CTCAE.

Exploratory analyses will also be performed on other safety parameters, as deemed appropriate, and within subgroups defined by age, sex, race, mutation status, prior therapies, medical history, and other prognostic factors. Exploratory analyses may also be performed on previously collected laboratory analytes, including PK samples.

Exposure to study treatment over time will be summarized with time on treatment, total amount of administered treatment, dose intensity and relative dose intensity.

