4.13 Treatment Compliance

Template: WCT-TP-ST-005-005 Page 15 of 24 Effective Date: 15-Apr-2016 Confidential

A participant is considered compliant with the study protocol when study medication is administered at a compliance level of ≥80% (excluding dose holds for surgical operations or drugrelated AEs). Treatment compliance will be calculated overall as follows:

(Total [cumulative] amount of treatment actually taken [mg])/Total [cumulative] amount of treatment that should have been taken [mg]) x 100

The total (cumulative) amount of treatment actually taken (mg) will be calculated as described in Section 4.12. The total (cumulative) amount of treatment that should have been taken (mg) will be calculated for each dose strength received as dose strength * (end date at that dose level – start date at that dose level) + 1 day, summed across all dosing records available for a participant.

Compliance will be summarized by Part, Cohort, and overall using the Safety Population. A listing of this data will also be provided.

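### SAP 4.12 produces neither dose intensity nor relative dose intensity in the usual sense, and no ratio in the plan captures dose lost to reductions, drug-related holds or non-escalation

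*SAP*

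**What the plan says.** Protocol 9.4 commits to four exposure summaries: "Exposure to study treatment over time will be summarized with time on treatment, total amount of administered treatment, dose intensity and relative dose intensity". It defines none of them, and Protocol 9.1 leaves details to the SAP.

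SAP 4.12 handles them as follows.

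- **Total amount:** capsules dispensed less those lost or returned, in mg, reported in this form: "sum of the total amount of 5 mg and 10 mg doses received across all cycles and for the entire study duration". It is a capsule-count total.
- **Relative dose intensity:** "Relative dose intensity (expressed in mg/m²) will be summarized using descriptive statistics". There is no formula. The table gives the "number and percentage of participants receiving at least one dose at each level".
- **Dose intensity:** "Dose intensity (expressed in mg) is defined as the total dose received, calculated using relative dose intensity and BSA".
- **Duration:** first to last dose, with interruptions ignored (also SAP 4.3.4).

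SAP 4.13 defines compliance as "Total [cumulative] amount of treatment actually taken [mg])/Total [cumulative] amount of treatment that should have been taken [mg]) x 100". The denominator is built from the dose and dates of each dosing record. Holds for surgery or drug-related AEs do not count against the 80% criterion.

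The only specific change from the protocol that SAP section 7 declares is the compliance formula.

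**The concern.** Dose intensity usually means dose per unit time, and relative dose intensity usually means delivered dose over planned dose. SAP 4.12 attaches these names to a total in mg and to a level in mg/m². A protocol that lists the two beside total amount evidently expects three different quantities, but the SAP supplies one quantity twice and a dose level.

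Since Amendment 7, safety and tolerability are the only study objective. How much of the scheduled dose participants could take is a basic measure of tolerability. Without it, a report can show near-complete compliance for participants who were reduced, held or never escalated because of toxicity, and give no figure for the dose they lost.

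**Working it through.** The plan states no figure on this point to reproduce. The check is one of units, followed by a worked example.

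**1. Units in SAP 4.12.** A daily level in mg/m² multiplied by BSA in m² gives mg per day. It becomes a total only after multiplication by days on dose, and 4.12 does not mention that step. If the step is added, the result is total mg, the quantity already obtained from capsule counts.

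**2. What the dose-level table can show.** It counts anyone with at least one dose at a level. A participant escalated from 15 to 25 mg/m² who stayed there, and one later reduced to 15, both count once at 15 and once at 25.

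**3. Worked example.** Inputs:

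- BSA 1.0 m² throughout (assumption). Protocol Appendix 2 gives 15 mg at the 15 mg/m² level and 25 mg at the 25 mg/m² level.
- Part B Cohorts 1-3 schedule from Protocol 6.3: three 28-day cycles at the first level, then the second.
- 12 cycles = 336 days, with every assigned capsule taken (assumption).

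Scheduled total = 84 × 15 + 252 × 25 = 1260 + 6300 = 7560 mg. Scheduled mean = 7560 / 336 = 22.5 mg/m²/day.

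Delivered mg:

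- Reduced from Cycle 7: 84 × 15 + 84 × 25 + 168 × 15 = 5880.
- Same, with a 21-day hold before restart: 84 × 15 + 84 × 25 + 147 × 15 = 5565.
- Never escalated: 336 × 15 = 5040.

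| Course | Delivered mg | mg/m²/day | Delivered / scheduled | SAP 4.13 compliance |
|---|---|---|---|---|
| Reduced 25 to 15 mg/m² from Cycle 7 | 5880 | 17.5 | 77.8% | 100% |
| Same, with 21-day hold | 5565 | 16.6 | 73.6% | 100% |
| Never escalated | 5040 | 15.0 | 66.7% | 100% |

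The compliance column places the extra day inside the bracket of the 4.13 denominator. Read literally, with the day added after the product, the values are 100.9%, 100.9% and 100.3%. For the never-escalated course, 5040 / (15 × 335 + 1) = 5040 / 5026.

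The hold row also assumes that hold days lie outside the dosing records, in line with the exclusion in the 80% criterion. If they lay inside the 15 mg record, compliance would be 5565 / 5880 = 94.6%, still far from 73.6%.

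**4. Can the two mg totals differ?** If mg/m² means the nominal level, nomogram rounding separates them. Level × BSA against the Appendix 2 dose:

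- 15 mg/m², BSA 0.50: 7.5 vs 10 mg, -25%.
- 15 mg/m², BSA 0.49: 7.35 vs 5 mg, +47%.
- 25 mg/m², BSA 0.33: 8.25 vs 10 mg, -17.5%.
- 25 mg/m², BSA 1.77: 44.25 vs 45 mg, -1.7%.

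The first three are cell-edge extremes. On an assumed uniform grid of BSA from 0.33 to 1.77 in steps of 0.01, the mean absolute gap is 9.8% on the 15 mg/m² row and 5.7% on the 25 mg/m² row. The mean signed gaps are +1.9% and -0.3%.

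**The case against.** A reader might infer that delivered versus planned dose is never reported. That goes too far: SAP 4.13 defines a taken-over-expected ratio in mg, summarizes it by Part, Cohort and overall, and lists it. But it measures adherence to whatever dose is assigned at the time, so the denominator falls with every reduction.

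A reader might also infer that the SAP breaches a protocol formula. It does not, because Protocol 9.4 names the two measures without defining them. The mismatch is with their usual meaning and with their listing as items separate from total amount.

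Nor do the documents show that the two mg totals must disagree. Appendix 2 also defines an actual mg/m² dose, namely actual mg over BSA. If 4.12 means that, multiplying by BSA returns the actual mg and the rounding gap vanishes. The SAP does not say which it means. A large gap computed at BSA 2.5 (62.5 vs 45 mg, +39%) would also overlook Protocol 6.3, which caps dosing above 1.77 m².

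Two further arguments have weight. Escalation is conditional, so a participant who stays at the starting level after toxicity is following the protocol; a ratio of 67% describes dose received, not a fault. And the AE endpoint is descriptive, with related information elsewhere: AEs by dose within cohort, withdrawals by dose at withdrawal, and listings of TEAEs that led to interruption or discontinuation. None of these quantifies lost dose, and SAP 4.16 names no output for dose reductions.

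**Conclusion.** The concern holds in this form. Under SAP 4.12, neither dose intensity nor relative dose intensity is produced in its usual sense. One repeats the cumulative total by a route whose units do not close, and the other is a dose level. SAP 4.13 does not fill the gap, because it compares delivered dose only with the dose currently assigned.

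In the example, 67% to 78% of the scheduled dose is delivered while compliance is about 100%. The size depends on the assumed BSA, the 12-cycle horizon, full intake of assigned capsules and, for the hold, how the dosing records are kept. The direction for reductions and non-escalation does not depend on these. Disagreement between the two mg totals is possible, not established.

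The plan should be changed because tolerability is all the study now assesses and the correction is cheap. The AE analyses themselves are unaffected.

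**What to change.** In SAP 4.12:

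- **Dose intensity** = cumulative mg from capsule counts / days from first to last dose, holds included, in mg/day. The duration already defined in SAP 4.3.4 serves as the denominator. Also give mg/m²/day, dividing the mg in each dosing interval by the BSA in force in that interval.
- **Relative dose intensity (%)** = 100 × cumulative mg taken / cumulative scheduled mg over the same days. Scheduled mg is the Appendix 2 nomogram dose for the scheduled level at the BSA in force, so rounding and the 45 mg ceiling cancel. Dividing by nominal mg/m² instead would score a fully adherent participant at 15 mg/m² as 10 / 7.5 = 133% (BSA 0.50) or 5 / 7.35 = 68% (BSA 0.49).
- **Reference schedule:** state it for Part B Cohorts 1-3; for Part A, where an increase was permitted after 3 or 6 cycles and the first six participants had a different escalation path; and for Cohort 4, using the enrolment dose for those on drug at entry. Show participants who did not escalate separately.
- **Housekeeping:** drop the second mg total, keep the at-least-one-dose table under the title 'dose levels received', and record the definitions in SAP section 7.

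Scheduled mg needs a single rule above BSA 1.77 m². Protocol 6.3 caps dosing there, while the 15 mg/m² row of Appendix 2 continues to higher BSA; those passages must be reconciled.

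The cost is SAP wording and programming. Capsule counts, dosing dates and BSA are already collected.
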